11.1.4.4 Pharmacodynamics

Pharmacodynamic variables based on blood samples and biopsy samples will be summarized using descriptive statistics (n, mean, standard deviation, median, minimum, maximum) by cohort. Summaries of change from baseline and percent change from baseline will also be presented for pharmacodynamic variables by cohort.

11.1.5 Methods of Analysis

Descriptive and inferential statistics will be used to summarize the data. Continuous variables will be summarized by n, mean, standard deviation, median, minimum and maximum values. Categorical variables will be summarized by subject counts and related percentages.

On an exploratory basis, common statistical methodology for response rates and survival time analysis may be applied. Counts and percentages, with their corresponding exact 95% confidence interval, will be calculated for the binomial endpoints (i.e., response rate).

Logistic regression analyses may be used to test potential predictive factors for overall response. A more detailed description of the statistical methods will be provided in a separate SAP.

11.1.6 Safety Variables

The DLTs occurring during Phase 1 will serve as the basis for the selection of the RP2D. Number and percentage of subjects with and without DLT will be presented according to DL and group.

Safety will be assessed on the basis of AE reports, clinical laboratory data, vital signs, ECGs, physical examinations and ECOG performance status. All safety summaries will be presented by total and DL for Phase 1, and total and group for Phase 2. The number of subjects experiencing each AE will be summarized by the MedDRA system organ class, MedDRA preferred term, and NCI CTCAE grade. In addition, the incidence, severity, seriousness, and relationship to study treatment of AEs will be tabulated. Serious adverse events and irAEs will be summarized separately.

Hematology, clinical chemistry, autoimmunity, infectious disease, vital signs, and ECG data will be listed individually by subject and suitably summarized. For all laboratory variables, which are included in the current version of NCI CTCAE, the CTCAE grade will be calculated. Summary statistics of mean, median, standard deviation, minimum, maximum and

number of observations will be used and changes from baseline will also be presented. For urinalysis parameters, any qualitative assessments will be summarized for all subjects using the number of subjects with results of negative, trace or positive. For laboratory data, abnormal values will be flagged in the data listings.

Adverse events will be listed individually by subject, DL, and group. Adverse event listings will also be presented by subject, system organ class, and preferred term.

Details of any deaths will be listed for all subjects. Deaths due to the study disease, toxic deaths and early deaths as well as the date of death as reported on the Death Form will be listed and summarized by DL and group.

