
Statistical Analysis
	
Descriptive and inferential statistics will be used to summarize the data. Continuous variables will be summarized by number, mean, standard deviation, median, minimum and maximum values. Categorical variables will be summarized by subject counts and related percentages.
 
Two subject populations will be used for the analyses.
 
The safety population will consist of all subjects who received at least 1 dose of RGT100-PEI.
 
The evaluable population will consist of all enrolled subjects who complete Week 4 or withdraw early for experiencing a DLT.
 
Safety will be assessed on the basis of AE reports, clinical laboratory data, vital signs, body weight, ECG, physical examinations and ECOG performance status. All safety summaries will be presented by total and dose level (DL) for the dose escalation phase and total and group (tumor-specific group) for the expansion phase. The number of subjects experiencing each AE will be summarized by the Medical Dictionary for Regulatory Activities (MedDRA) system organ class, MedDRA preferred term, NCI CTCAE grade and relationship to study treatment. Serious adverse event and irAEs will be summarized separately.
 
Summary statistics (mean, median, standard deviation and range as appropriate) by cohort, group and overall will be presented for vital signs, physical examination findings, ECG parameters and clinical laboratory tests (clinical chemistry, hematology, cytokines and urinalysis) with changes from baseline also presented. For laboratory data, abnormal values will be flagged in the data listings. All safety data will be included in the subject data listings.
 
On an exploratory basis, common statistical methodology for response rates and survival time analysis may be applied. Counts and percentages, with their corresponding exact 95% confidence interval, will be calculated for the binomial endpoints (i.e., response rate). Logistic regression analyses may be used to test potential predictive factors for overall response.

	
Plasma concentrations of RGT100-PEI will be summarized by cohort and group using descriptive statistics (number, geometric mean, arithmetic mean, standard deviation and coefficient of variation [CV], minimum, maximum) at each timepoint.

--	---

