8.4.8 Maximum Tolerated Dose, Maximum Feasible Dose, and RP2D

The MTD is defined as 1 DL below the DL where ≥ 2 of 6 subjects in a group experience a DLT for RGT100-PEI during the DLT period of 4 weeks. Maximum tolerated dose will be determined following discussion of all the relevant toxicity data by the SRC during the dose escalation meetings after each dose escalation step (refer to [Section 10.5](#) for SRC details).

If ≤ 1 of 6 subjects in all dose levels experience a DLT, then an MTD will not have been reached in this group. In this case, the RP2D will be selected based on integrated evaluation of safety, tolerability, clinical benefit, and pharmacodynamic data, for all DLs tested.

Once the MTD has been defined, dosing at a higher dose must not occur in this group. Once the MTD has been exceeded, the cohort at the next lowest DL will be expanded to 6 subjects if necessary and only 3 subjects were involved before. The SRC are free to decide on an intermediate DL.

The MFD is the highest dose volume that is safe and tolerable, and is feasible for intralesional/intratumoral injection in the respective group. The MFD may be lower than the MTD. The MTD (or MFD if lower than MTD) will define the RP2D to be used in the expansion phase of the study.

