8.4.9 Selection and Timing of Dose for Each Subject

8.4.9.1 Dose Escalation Phase

The planned DLs to be investigated are presented in Table 2 below.

Table 2: Dose Levels for RGT100-PEI Dose Escalation

Dose Level	RGT100-PEI Dose	Volume of RGT100-PEI to be Injected
1	0.2 mg	1 mL
2	0.4 mg	2 mL
3	0.6 mg	3 mL
4	0.8 mg	4 mL

RGT100-PEI will be administered by intratumoral/intralesional injection. A dose escalation meeting with the SRC (refer to [Section 10.5](#) for SRC details) will be held to evaluate a dose escalation after all subjects in a DL per group have completed the DLT period.

Group A: Dosing for Group A (cutaneous lesions) will start first. The total dose will be administered each on 2 separate days of every week (Mondays and Thursdays or Tuesdays and Fridays) for a maximum of 4 weeks.

Group B: Dosing for Group B (liver lesions) will start once DL2 has proven to be safe in Group A. Dosing in Group B will then start at DL2. The total dose will be administered on 1 day of every week for a maximum of 4 weeks.

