11.1.2.1 Dose Escalation

All evaluable subjects will be analyzed for dose escalation, which are those completing Week 4 or those withdrawing early for experiencing a DLT. Number and percentage of subjects with and without DLT will be presented according to DL.

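### The general Phase 1 rule leaves the escalation-phase AE, SAE and irAE incidence tables without a Group A/B split, so read literally the DL2 to DL4 columns mix two routes and schedules.

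*Combined protocol and SAP*

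**What the plan says.** The general rule in 11.1.6 (Safety Variables) is: "All safety summaries will be presented by total and DL for Phase 1, and total and group for Phase 2". The synopsis agrees: "All safety summaries will be presented by total and dose level (DL) for the dose escalation phase". In the synopsis, the word group in that rule belongs to the expansion phase and means the tumor-specific group.

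Several outputs have a more specific rule:

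- **DLTs, 11.1.6:** "Number and percentage of subjects with and without DLT will be presented according to DL and group".
- **DLTs, 11.1.2.1:** "Number and percentage of subjects with and without DLT will be presented according to DL", with no mention of group.
- **Deaths, 11.1.6:** "as well as the date of death as reported on the Death Form will be listed and summarized by DL and group".
- **AE listings, 11.1.6:** "Adverse events will be listed individually by subject, DL, and group".
- **Discontinuation reasons (11.1.3.1) and dose interruptions or delays (11.1.3.2):** by DL and group.
- **Laboratory tests, vital signs, physical examination and ECG (synopsis):** by cohort, by group and overall.

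The AE, SAE and irAE incidence tables have no such rule. Section 7.2 lists the incidence and severity of treatment-related AEs, and the occurrence of SAEs, among the primary endpoints.

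On dosing, 8.4.9.1 says for Group A: "The total dose will be administered each on 2 separate days of every week". Group B is dosed on one day per week and starts at DL2. Section 8.4.8 defines the MTD from the number of subjects with a DLT within one group: "of 6 subjects in a group experience a DLT for RGT100-PEI during the DLT period of 4 weeks".

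**The concern.** A dose level is a dose per injection day. It does not identify a treatment, because the two groups differ in injection site and in frequency. A table by DL alone treats them as one stratum.

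The tables affected may matter for dose selection. Section 8.1.1 does not expect an MTD at the planned levels. If none is reached, 8.4.8 bases the RP2D on an integrated assessment that includes safety and tolerability, and 8.1.2 requires a safety report that justifies the RP2D to authorities. Some toxicity can appear only in the AE and irAE tables: 8.4.7 excludes from the DLT definition grade 3 tumor flare and grade 3 irAEs that resolve to grade 1 or lower within 7 days.

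A liver-specific pattern is the one most worth seeing separately. Section 6.4 states that local toxicity after direct liver injection was not studied nonclinically, and 6.6 names altered liver function as a potential risk.

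**Working it through.** **1. Injections per cycle.** Frequency × 4 weeks gives 2 × 4 = 8 in Group A and 1 × 4 = 4 in Group B. This reproduces Tables 3 and 4 (injections 1–8 and 1–4).

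**2. Planned cycle dose.** Injections × dose per injection (Table 2):

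| DL | Group A | Group B |
|---|---|---|
| 1 | 8 × 0.2 = 1.6 mg | none (starts at DL2) |
| 2 | 8 × 0.4 = 3.2 mg | 4 × 0.4 = 1.6 mg |
| 3 | 8 × 0.6 = 4.8 mg | 4 × 0.6 = 2.4 mg |
| 4 | 8 × 0.8 = 6.4 mg | 4 × 0.8 = 3.2 mg |

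At every shared level the ratio is 2. Group B at DL4 has the same planned cycle dose as Group A at DL2, so DL order is not cycle-dose order once the groups are mixed.

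**3. Who is in each column.** The 3+3 scheme gives 3 to 6 evaluable subjects per DL and group. A DL-only table then holds 3 to 6 subjects at DL1 (all Group A) and 6 to 12 at each of DL2 to DL4 (both groups).

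**4. Effect on a trend (hypothetical rates).** Suppose an AE occurs in 10% of Group A and 30% of Group B at every dose level, so dose has no effect in either group. The expected DL1 column is 10%. With 6 subjects per group, the DL2 column is (6 × 0.10 + 6 × 0.30)/12 = 20%. With 3 from A and 6 from B, it is (3 × 0.10 + 6 × 0.30)/9 = 23%. The apparent rise from DL1 to DL2 comes only from Group B entering the table.

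**5. Effect on one column (hypothetical counts, non-DLT event).** Clopper–Pearson 95% intervals:

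| Subjects | Events | Rate | 95% CI |
|---|---|---|---|
| Group A | 0/6 | 0% | 0–46% |
| Group B | 2/6 | 33% | 4–78% |
| Combined | 2/12 | 17% | 2–48% |

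The combined row describes neither group. The example is restricted to non-DLT events because 11.1.6 already splits DLTs by group.

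**6. Rules side by side.** Two conflicts remain after each output is matched to its rule:

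- The general rule (total and DL) against the synopsis sentence that adds group for laboratory, vital-sign, physical-examination and ECG summaries.
- 11.1.2.1 (DLTs by DL) against 11.1.6 (DLTs by DL and group).

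The AE, SAE and irAE incidence tables fall under the general rule alone.

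**The case against.** The strongest reply is that dose decisions do not depend on these tables. That largely stands. Section 8.4.7 requires safety data per DL and per group before the next enrolment decision. Section 8.4.9.1 holds the dose escalation meeting after a DL is complete within a group. Section 8.4.8 defines the MTD within a group, and 10.5 gives the Safety Review Committee listings of the subjects' safety data. A reader might infer that the MTD would be set from pooled data; the documents do not support this. Where no MTD is reached, safety data do enter the RP2D choice, but nothing says the combined incidence tables would be the source.

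A reader might also infer that all escalation-phase safety tables are by DL alone. That is contradicted by the DLT and death rules in 11.1.6, by 11.1.3.1 and 11.1.3.2, and by the synopsis sentence on laboratory and other summaries. In that last sentence, however, it is arguable whether group means A/B or the tumor-specific group.

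Finally, pooling is an inference. No sentence says A and B will be combined. Each group has its own escalation phase (8.1), so by DL could be meant within group. The detailed analysis plan announced in 11.1 and 11.1.5 is not in the document reviewed and may settle the layout. This lowers certainty about intent but does not remove the point. The same section writes DL and group where it wants both, and 11.1.7 rules out subgroup analysis for the escalation phase. AE listings by group allow counts to be rebuilt, but they do not replace a primary-endpoint table.

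**Conclusion.** The point holds in a limited form. A stated rule, followed as written, leaves the escalation-phase AE, SAE and irAE incidence tables without a Group A/B split. At DL2 to DL4 it would then mix two injection sites, two schedules and a twofold difference in planned cycle dose, while DL1 stays Group A only. This affects the interpretability of primary-endpoint reporting; it is not a flaw in the escalation rules. The two internal conflicts, on DLTs and on laboratory and related summaries, are drafting inconsistencies to be reconciled.

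The conclusion assumes the general rule is applied literally and the full planned schedule is given. The size of any masking is unknown: the counts and rates in steps 4 and 5 are illustrations, and the twofold dose difference is not itself evidence of hidden toxicity. The change should be made before the table shells are fixed.

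**What to change.** State in 11.1.6 that all escalation-phase safety summaries, in particular the AE, SAE and irAE incidence tables, are presented by DL within Group A and by DL within Group B, with a total for each group. Any combined A and B column should be labelled supplementary.

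Align the general rule in the synopsis with this. Define there what group means in the sentence on laboratory, vital-sign, physical-examination and ECG summaries. Add the group split to the DLT sentence in 11.1.2.1 so that it agrees with 11.1.6, and carry the layout into the separate SAP and table shells.

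No new data, subjects or visits are needed. The cost is more columns, each with 3 to 6 subjects, so percentages will be coarse and counts should be shown beside them.

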11.1.7 Sub-group Analysis

No subgroup analysis will be performed for the dose escalation part of the trial. Clinical safety and activity will be assessed in the escalation phase in order to decide on the indications for the expansion groups.

A safety report will be completed at the end of the dose escalation phase.

A SRC will meet to review the safety results from a given cohort before escalating to the next dose in a new cohort.

11.1.8 Handling of Missing Data

Missing data will not be replaced. Analyses will be performed considering all data observed for the respective analysis sets. For missing AEs and concomitant medication start and end dates the followings rules will be applied:

Partial/missing start date:

- Missing day: Impute the first of the month unless month is same as month of first dose of study drug then impute first dose date
- Missing day and month: impute 1st January unless year is the same as first dose date then impute first dose date
- Completely missing: impute first dose date unless the end date suggests it could have started before this in which case impute the 1st January of the same year as the end date.

Partial/missing end date:

- Missing day: Impute the last day of the month unless month is same as month of last dose of study drug then impute last dose date
- Missing day and month: impute 31st December unless year is the same as last dose date then impute last dose date

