8.4.11 Prior and Concomitant Therapy

Concomitant medication may be given as medically indicated. All subjects will be asked to provide a complete list of concomitant medication including prescription, over-the-counter, complementary, and alternative medications that have been taken within 4 weeks before the first treatment visit. They must also inform the Investigator about any new medication started while on the trial.

Details (including indication, doses, frequency, and start/stop dates) of concomitant medication taken during the trial, until the completion of the end of treatment visit, must be documented in the medical record and the appropriate eCRF.

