10.4 Safety Variables

10.4.1 Adverse Events

10.4.1.1 Adverse Event Definition

An AE is defined as any untoward medical occurrence in a clinical study subject administered a medicinal product which does not necessarily have a causal relationship with this treatment. An AE can therefore be any unfavorable and unintended sign (including an abnormal laboratory finding), symptom, or disease temporally associated with the use of a medicinal (investigational) product, whether or not it is related to the medicinal (investigational) product. This includes an exacerbation of pre-existing conditions or events, intercurrent illnesses, drug interaction or the significant worsening of the indication under investigation that is not recorded elsewhere in the eCRF under specific efficacy assessments. Anticipated fluctuations of pre-existing conditions, including the disease under study that do not represent a clinically significant exacerbation or worsening need not be considered AEs.

The Investigator will monitor each subject for clinical and laboratory evidence of AEs on a routine basis throughout the study. Should an Investigator become aware of any study drug-related SAEs following this period these must also be reported as stated in [Section 10.4.4.3](#). Adverse event monitoring starts from the time the subject consents to the study until they complete the trial. All reportable AEs will be followed to a satisfactory conclusion. Any reportable drug-related AEs that are unresolved at the follow-up visit are to be followed up by the Investigator until resolution or stabilization.

AEs will be elicited by asking the subject a non-leading question, for example, “Have you experienced any new or changed symptoms since we last asked/since your last visit?” AEs should be reported on the appropriate page of the eCRF.

Each separate AE episode must be recorded. For example, if an AE resolves completely or resolves to baseline and then recurs or worsens again, this must be recorded as a separate AE. For AEs to be considered intermittent, the events must be of similar nature and severity.

Tumor progression is not an AE. However, the medical conditions associated with disease progression must be documented as AE.

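### Partial start dates in 11.1.8 are set to the first-dose date without checking for an earlier known end date, and 11.1.6 counts pre-dose events at a dose level

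*Combined protocol and SAP*

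**What the plan says.** Section 11.1.8 states its scope as "For missing AEs and concomitant medication start and end dates the followings rules will be applied". It then gives three rules for start dates:

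- Day missing: day 1 of the recorded month is used, "unless month is same as month of first dose of study drug then impute first dose date".
- Day and month missing: "impute 1st January unless year is the same as first dose date then impute first dose date".
- No date at all: the first-dose date is used, except that an end date pointing to an earlier onset leads to 1 January of that end date's year.

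Only the third rule refers to the end date.

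Pre-dose records are part of the design. Section 10.4.1.1 says "Adverse event monitoring starts from the time the subject consents to the study until they complete the trial", and section 9 allows screening of up to 3 weeks. Section 8.4.11 asks for medications "that have been taken within 4 weeks before the first treatment visit".

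For reporting, section 11.1.6 says "The number of subjects experiencing each AE will be summarized by the MedDRA system organ class", among other breakdowns. It presents safety summaries by dose level in the escalation phase and summarises serious AEs separately. It sets no time window relative to the first injection. The safety population in 11.1.2 selects subjects who were dosed; it does not select events. Section 7.2 makes the occurrence of serious AEs a primary endpoint, with no condition on relatedness.

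**The concern.** There are two linked gaps.

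First, the date rules are not consistent with each other. A record with no start date at all is checked against its end date. A record with a known month or year, which carries more information, is not. A screening event or a short course of prior medication that is known to have ended before the first injection can therefore be given a start on the first-dose day. Its duration is then negative, and it appears to begin with treatment.

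Second, the AE tables have no cut at the first injection. Events in the screening period, including any from the mandatory baseline biopsy that 10.3.2 allows up to 48 hours before the first injection, are counted at a dose level although no drug had been given.

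The gaps interact. If an on-treatment cut is added later and the date rule is left alone, the rule will carry already-ended screening events across that cut.

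**Working it through.** The plan gives no figure on this point, so there is none to reproduce. All dates below are illustrative.

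**1. The rules applied literally.** First dose is 20 March 2017.

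- Start recorded as March 2017, known end 10 March. The month matches, so the imputed start is 20 March, which is 20 − 10 = 10 days after the end.
- Start recorded as 2017 only, known end 10 February. The year matches, so the imputed start is 20 March, which is 18 + 20 = 38 days after the end.
- Start completely missing, known end 10 March. The end date shows an earlier start, so the imputed start is 1 January 2017, which precedes the end.

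**2. How often a screening AE shares the month of first dose.** Let first dose fall on day d of a 30-day month, each d equally likely, and let onset be uniform over the w days before it. Of those w days, min(d − 1, w) lie in the same month.

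- w = 21 (the longest screening period): the sum over d is (0 + 1 + … + 21) + 8 × 21 = 231 + 168 = 399. The share is 399 / (30 × 21) = 0.633.
- w = 7 (assumed, for a short screening): 28 + 22 × 7 = 182. The share is 182 / (30 × 7) = 0.867.

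So 63% belongs to the full window, and a shorter screening raises it.

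**3. How often the result is impossible.** Some moved events end after first dose, and moving those is defensible. The defect is confined to events with a known end before first dose. Taking every first-dose date in a 365-day year and every onset in the preceding 21 days gives 365 × 21 = 7,665 records. The end is taken as onset plus duration minus 1 day, and the durations are assumptions. The rules move 64% of day-missing and 97% of year-only records to the first-dose date. The imputed start falls after the known end as follows:

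| Duration (days) | Day missing | Day and month missing |
|---|---|---|
| 1 | 64% | 97% |
| 3 | 55% | 88% |
| 7 | 39% | 69% |
| 14 | 16% | 36% |

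The denominator is screening AEs with that kind of partial start date, not all AEs. If records whose known end precedes first dose are instead given the first of the recorded month, or 1 January of the recorded year, every column falls to 0.

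**4. Medications.** No share is given. Section 8.4.11 asks for medications taken in the 4 weeks, not started in them. A long-standing drug begun in an earlier month or year is not moved to first dose by these rules.

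**5. The missing reporting cut.** One subject in an escalation cohort of 3 to 6 is 1/6 = 17% to 1/3 = 33%. Under 11.1.6, a subject whose only serious AE occurred in screening adds that much to the serious AE incidence at the assigned dose level.

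**6. The mirror gap.** In 11.1.8, an end date missing its day becomes the last-dose date when the month matches last dose. With last dose on 10 March, a known start of 20 March and an end recorded as March, the imputed end is 10 March, 10 days before the start. Section 10.4.1.7 collects events for 30 or 60 days after the last dose, so such records can arise.

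**The case against.** The strongest reply is that the date rule does not alter any count. Since 11.1.6 has no on-treatment cut, a screening event is tabulated whatever start it is given. That stands. A reader might infer that the imputation inflates AE or serious AE incidence, or makes events treatment-emergent. The documents define no such class, so the 17 to 33 points belong to the missing reporting cut and not to the date rule.

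It can also be said that most primary endpoints are insulated. Treatment-related AEs and related discontinuations rest on the investigator's causality judgement (10.4.1.4), and nothing ties that judgement to an imputed date. Dose-limiting toxicities must be drug-related and fall in the DLT period (8.4.7), and the Safety Review Committee reviews safety data during the trial (10.5). This stands too. Serious AE occurrence is the exception, because 7.2 attaches no relatedness condition to it.

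Partial AE dates should be few: 10.4.1.8 requires onset and resolution dates, 10.4.4.3 requires serious AEs to be reported within 24 hours of awareness, and 12.4 has missing or inconsistent data queried. These controls reduce the problem, but 11.1.8 exists for the dates that remain missing.

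Using the first-dose date when timing is uncertain is a usual conservative choice. That is accepted where the end date is unknown or falls on or after first dose. It does not justify overriding a known earlier end. Finally, 11.1 and 11.1.5 promise a more detailed SAP, which may close both gaps; the rules in 11.1.8 are the only ones available here.

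**Conclusion.** The point holds in two parts. As written, 11.1.8 can give a pre-dose record a start after its own known end, because two of its three start-date rules lack the check that the third has. As written, 11.1.6 counts AEs and serious AEs that began before any drug at a dose level.

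About 63% of screening AEs with a missing start day would be moved to first dose, assuming uniform timing and a full 21-day screening period. The share that becomes impossible depends on duration and was 16% to 64% for the durations tried. How many dates will be partial is not known, so the absolute number could be small. The reporting gap is worth 17 to 33 percentage points per affected subject in a cohort of 3 to 6.

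A reader might go further and conclude that dose escalation or the recommended dose is affected. The documents do not support that: those decisions rest on drug-related toxicities reviewed during the trial, and 11.1.8 has no stated part in them.

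**What to change.** In the SAP:

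1. In both partial-start-date rules, if the known or latest possible end date is before first dose, impute the first of the recorded month, or 1 January of the recorded year when the month is missing. For AEs the imputed date must not precede consent, and it must never fall after the end date. Otherwise keep the first-dose date.
2. Add the mirror check, so that an imputed end date is never before a known start.
3. Summarise AE and serious AE incidence by dose level for events starting or worsening on or after the first injection, and list events between consent and first injection separately.

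Item 3 needs a stated convention for worsening. Section 10.4.1.3 keeps one record at the highest grade, and 10.4.1.2 keeps the first onset date when an event later becomes serious. A cut on onset date alone would therefore drop a screening event that became severe or serious after dosing. Where the record cannot show when that happened, an event still ongoing at the first injection should be counted.

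The cost is SAP wording and programming. Section 11.1.1 already provides for recording departures from the protocol's planned analyses in the SAP.
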